3.7 Methods

Upon enrollment, patients will be randomized (2:1 distribution for intensive monitoring, stratified by STEMI vs. NSTEACS) to receive standard care or intensive monitoring. Intensive monitoring entails wearing a Spiderflash (LivaNova) 30-day external cardiac monitor at discharge. A 30-day external cardiac monitor represents the most feasible, high-quality, non-invasive monitoring strategy possible, while maximizing the duration of uninterrupted monitoring beginning at discharge. Demographics, clinical characteristics, and risk factors for stroke and bleeding (i.e. CHADS₂, HASBLED) will also be collected at enrollment.

The research team will perform all aspects of SpiderFlash data acquisition and interpretation. The research team has purchased the SpiderFlash devices and the programming/analysis software. After patients have completed the 30-day recording, the information will be downloaded directly off the device (via SD card). There is no

industry involvement and no data transfer to a server or out of country. There is no relationship between the SpiderFlash provider and UBC/VCH, and no connection between the research team and SpiderFlash provider. All funds are provided by a research award attained by the trainee (CC).

Spiderflash ECGs will be interpreted by the trainee (CC, cardiology resident) with oversight from the supervising physician (JA). The reports will be distributed to the primary cardiologist and family physician. The standard care strategy includes a 12-lead ECG performed prior to discharge and at follow-up with the primary cardiologist (typically 4-8 weeks post-MI).

Cardiac medication review will be performed by the trainee (CC) at 90-days and 1-year post-monitoring (to allow adequate time for anticoagulant initiation). A telephone follow-up (15 min) and chart review will confirm anticoagulation status, and reasons for initiating or withholding anticoagulation.

Both the intensive monitoring and control groups will receive telephone follow-up at 90days to assess prescription status. No additional care or clinic visits are scheduled for the control group. All additional data (including ECGs performed by primary cardiologist and confirmation of anticoagulation status) in the intervention and control group will be performed via electronic chart review of Cardiology EMR.

3.8 Sample Size Calculations and Statistical Analysis

Previous retrospective and cohort data has identified new-onset AF in 7-14% of patients in-hospital or within 2 days after MI.^{4, 21} Between 3-30 days, new AF occurs in 3.7% when ascertained through an electronic ECG database, with the remainder of AF (12%) developing during long-term follow-up (6.6 years).²¹ Thus, at 30-days post-MI, we anticipate that the standard care strategy will detect similar rates of AF to this cohort study (3.7%).

Using an ILR, new-onset AF was detected in 16% at 2-months (approx. 8% at 1-month, CARISMA).⁵ However, in the CARISMA study, AF was only detected when HR \geq 125 bpm, effectively missing AF at slower rates (<125 bpm).⁵ Up to half of patients (49%) with AF post-MI have heart rates \leq 94 bpm.⁷ Thus, we anticipate that an intensive monitoring strategy (30-day external cardiac monitor) will detect higher rates of AF (16%) after 30-days (double ILR rate given the heart rate limitations).

With a 2:1 randomization to intensive monitoring and using a 5% significance level (α =0.05), **216 patients** (144 patients with intensive monitoring and 72 patients with standard care) are required to have a 80% power (1- β =0.80) of detecting an increase in new AF (primary outcome) from 3.7% (standard care) to 16% (intensive monitoring). Accounting for a 5% drop-out, the final sample size is **240 patients (120 patients per group)**.

Statistical analysis will be performed using an intention-to-treat analysis for patients randomized to the intensive monitoring or standard care strategy. Regression analysis

will be used to compare rates of AF at 30-days between both groups. Time-to-event analysis will be used to compare the time to development of AF in both groups.

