4. FEASIBILITY

4.1 Recruitment

There are approximately 310 STEMI/year in the health region (308-341/year, regional data²²) with at least 4 NSTEACS per 1 STEMI (1240 NSTEACS/year, including transfers, regional data²³). Patients will be excluded based on LVEF>40% (66% ineligible²⁴), pre-existing AF (9%²¹), in-hospital AF (14%⁴), LV thrombus (8%²⁵), and other factors (i.e. heart valves/VTE; uncommon, $\leq 1\%^{26}$). 368 patients/year will meet enrollment eligibility. Using an enrollment rate of 66%, 20 patients will be enrolled per month (10 for intensive) and the target (264 patients) will be met in 13 months.

Patient recruitment will be overseen by Cardiology Research Manager, [name], and Cardiology Clinical Research Coordinator, [name].

Patients will be recruited directly from the Vancouver General Hospital Coronary Care Unit (CCU). The Cardiology research nurses ([name] and [name]) routinely screen patients admitted to the CCU for study eligibility. This process is well-established for a number of ongoing studies that operate in the CCU.

In this study, prospective participants will be identified upon admission to the CCU meeting the eligibility criteria. Study participants will be approached by [name] and [name] for consent to participate in the study.

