4.2 Randomization and Blinding

Patients will be recruited from the Vancouver General Hospital Cardiac Care Unit (CCU) and St. Paul's Hospital Cardiac Intensive Care Unit (CICU). Randomization will be performed using a central randomization system (integration through RedCap) in a 1:1 manner, and will be implemented using an online access (RedCap) system. A back-up randomization will be available through sealed envelope in case of database issues. The allocation sequence will be generated by the co-investigator and Database expert (AS). Patients will not be blinded to the monitoring device. Physicians will blinded to patient identity, but will only review results for patients that received the monitoring device.

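### The plan allocates 2:1 in some sections and 1:1 in others, and its 5% drop-out step gives 240 (then 264) where the arithmetic gives 228

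*Combined protocol and SAP*

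**What the plan says.** **Allocation.** Section 3.7 (Methods) says "patients will be randomized (2:1 distribution for intensive monitoring, stratified by STEMI vs. NSTEACS". The power statement in section 3.8 agrees: "With a 2:1 randomization to intensive monitoring and using a 5% significance level", with "144 patients with intensive monitoring and 72 patients with standard care) are required to have a 80% power" to detect a rise in new AF from 3.7% to 16%. The sentence after it reads "Accounting for a 5% drop-out, the final sample size is" followed by "240 patients (120 patients per group", which is equal allocation. Section 4.2 (Randomization and Blinding) is explicit: "Randomization will be performed using a central randomization system (integration through RedCap) in a 1:1 manner".

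**Total.** Section 3.8 gives 216 before drop-out and 240 after it. Section 4.1 (Recruitment) plans that "20 patients will be enrolled per month (10 for intensive) and the target (264 patients) will be met in 13 months". Ten of 20 is again 1:1, and 264 is a third total.

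No section explains the move from 2:1 to 1:1 or from 240 to 264.

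**The concern.** The ratio has to be fixed before a single patient is randomised. Section 4.2 says "The allocation sequence will be generated by the co-investigator and Database expert". Whoever builds that list, and the sealed back-up envelopes, must contradict either 3.7 or 4.2. If the ratio is settled only after enrolment has begun, the design changes mid-trial.

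The enrolment end point is equally open: staff could stop at 240 or at 264 and cite the protocol for either. The stated power was worked out for 144:72, which is neither the design in 4.2 nor the final arm sizes in 3.8.

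**Working it through.** **Inputs.** Section 3.8 gives the AF rates (3.7% standard care, 16% intensive), the 5% significance level, 80% power, 144:72 and 5% drop-out. It does not give sidedness or the test behind the calculation. I assume two-sided 0.05 and the pooled two-proportion z test without continuity correction.

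**Step 1: reproduce 216.** With ratio k = 2 and weighted mean rate p̄ = (0.037 + 2 × 0.16)/3 = 0.119, the control arm size is

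n = [1.960 √(p̄(1−p̄)(1 + 1/k)) + 0.842 √(p₁(1−p₁) + p₂(1−p₂)/k)]² / (p₂−p₁)²

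= [1.960 × 0.3966 + 0.842 × 0.3207]² / 0.123² = 72.5, rounded up to 73.

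That is 73 + 146 = 219, and power at 72:144 is 79.7%. The stated 216 is therefore sound at 2:1. It does not by itself show which ratio was intended, because a 1:1 calculation with continuity correction gives 107 per arm, or 214.

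**Step 2: the drop-out step.**

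- 216/0.95 = 227.4, so 228 (152:76 at 2:1, 114:114 at 1:1).
- Multiplying instead, 216 × 1.05 = 226.8, so 227.
- Starting from 219, 219/0.95 = 230.5, so 231.
- 240 = 216/0.90, a 10% allowance.

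No route gives 240 at 5%. At 2:1, 240 would split 160:80, not 120:120.

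**Step 3: the 264 target.** 240/0.95 = 252.6, so 253; 216/0.95 gives 228. As an allowance on 216, 264 would be 1 − 216/264 = 18.2%. It also equals 240 × 1.10, but no such allowance is stated. It is not a stray digit: 4.1 has 368 eligible patients a year and 66% enrolment, so 368 × 0.66/12 = 20.2 a month, and 264/20.2 = 13.0 months, as stated.

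**Step 4: power of each reading.** Power = Φ[(0.123 − 1.960 × SE₀)/SE₁], where SE₀ uses the pooled rate and SE₁ the separate rates. For 72:144, SE₀ = 0.04673 and SE₁ = 0.03779, so Φ(0.831) = 79.7%. Fisher exact power is by full enumeration.

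| Standard : intensive | Reading | Pooled z | Fisher exact |
|---|---|---|---|
| 72:144 | 216 at 2:1, as stated | 79.7% | 79.4% |
| 76:152 | 228 at 2:1; also 240 at 2:1 less 5% | 82.1% | 82.4% |
| 80:160 | 240 at 2:1 | 84.3% | 85.0% |
| 114:114 | 228 at 1:1; also 240 at 1:1 less 5% | 88.1% | 85.7% |
| 120:120 | 240 at 1:1 | 89.7% | 87.6% |
| 132:132 | 264 at 1:1 | 92.3% | 91.1% |

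**The case against.** The contradiction itself has no good answer, but several points on the other side limit what follows from it.

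- **Power is adequate either way, and section 4.4 calls this a pilot.** True. The 228/240/264 mismatch alone would be a modest wording correction. The weight rests on the ratio.
- **If 2:1 is the real design, the stated power is nearly right.** Also true: 240 less 5% leaves 152:76 and 82.1%. The understatement is material only at 1:1. If the loss were 10%, as 240 implies, 2:1 would return to 144:72 and 79.7%.
- **2:1 has a claim to be the intended ratio.** It is in the Methods and is the only ratio with a power calculation. The choice belongs to the investigators. One practical fact bears on it: 4.3 and 4.6 provide 10 monitors, each worn for 30 days. Ten intensive starts a month fits that; 2:1 at 20 a month needs 20 × 2/3 = 13.3.
- **A revised timeline would inherit a doubtful rate.** The 20 a month in 4.1 comes after removing 66% of patients for LVEF above 40%, a criterion absent from 3.4 and 3.5. That is a separate defect, so any timeline should be conditional on it.
- **Section 3.8 plans regression, not a two-proportion test.** This is why the test behind the power figure has to be named.

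**Conclusion.** The concern holds. The current text contains two allocation ratios, a drop-out step that does not follow from its own 5%, and two enrolment targets, neither of which is the 228 that 5% implies. The excess over 228 is 12 patients in 3.8 and 36 in 4.1. With 240 patients, the ratio alone moves the standard care arm from 80 to 120.

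This is not a power shortfall. With 5% loss, 240 patients give about 82% at 2:1 and 88% at 1:1, and 264 gives more. These figures assume the protocol's rates, a two-sided 0.05 level and the pooled test. The contradictions in ratio and total do not depend on those assumptions. The point must be settled before the randomisation list is built, because the list cannot be made to match the protocol as written.

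**What to change.** State one ratio, one drop-out rate and one total in 3.7, 3.8, 4.1 and 4.2, and name the test and its sidedness, before the REDCap list and the back-up envelopes are generated. Either ratio can be made consistent.

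**If 1:1 (fewest changes):** change 3.7 and the power sentence in 3.8 to 1:1, and put in 3.8:

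> A total of 240 patients (120 in each arm) will be randomised 1:1. With 5% drop-out, 114 evaluable patients in each arm give about 88% power (two-sided 0.05, pooled two-proportion test; about 86% by Fisher exact) to detect 3.7% versus 16%.

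In 4.1, replace 264 with 240 and 13 months with 12 (240/20), provided the rate of 20 a month stands once the LVEF filter is reconciled with the eligibility criteria.

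**If 2:1:** state either 228 randomised (152:76), leaving about 216 evaluable and about 80% power, or 240 randomised (160:80), leaving 152:76 and about 82%. Then correct the per-group figure in 3.8, the monthly intensive count, target and timeline in 4.1, and the ratio in 4.2. Confirm that 10 monitors can support about 13 intensive starts a month, or lengthen the timeline.

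If the total is reconsidered at 1:1, do not cut it to the normal-approximation minimum of 91 per arm without naming the test, since Fisher exact power there is 75.7%.

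**Cost:** wording and one restated power figure. No extra patients are needed: 240 is already the stated final size and is 24 below the 264 in 4.1.

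### Randomisation is stratified by STEMI vs NSTEACS, but the primary regression is not stated to include that stratum

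*Combined protocol and SAP*

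**What the plan says.** Section 3.7 makes MI type a design factor: allocation is "stratified by STEMI vs. NSTEACS". The enrolment case report form (Appendix 1) records whether the infarction was STEMI or NSTEMI, so the stratum is known for every patient.

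Section 3.8 sets out the analysis in three sentences. The first fixes the population: "Statistical analysis will be performed using an intention-to-treat analysis". The second is the whole statement of the primary comparison: regression "will be used to compare rates of AF at 30-days between both groups". The third adds a time-to-event comparison of the two arms. None names a link function, an effect measure, a covariate or a stratum term, and no other section supplies one. Equally, none says that the model is unadjusted.

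Section 4.2, which describes how randomisation is carried out, mentions neither stratification nor blocking. It also gives a 1:1 ratio, against 2:1 in 3.7.

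**The concern.** Stratified allocation, when it balances the arms within strata, removes chance imbalance on MI type from the treatment comparison. An analysis without the stratum still counts that variability in its standard error. If MI type predicts AF, the standard error is then somewhat too large for the design, the confidence interval is slightly wide and the test rejects a little less often than its nominal level. A prognostic effect is plausible on the plan's own terms: objective 2b in 3.2 lists MI characteristics among the candidate risk factors for new AF.

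A little efficiency is at stake, in a design that the usual formula puts almost exactly at its 80% target. So is prespecification. With the model unnamed, the choice between an adjusted and an unadjusted analysis stays open until data are seen.

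**Working it through.** **Inputs.** From 3.8: AF 3.7% under standard care and 16% under intensive monitoring, alpha 0.05 (sidedness not stated; two-sided assumed), 80% power, 144 intensive and 72 standard care. From 4.1: about one STEMI to four NSTEACS, so a STEMI share of 20%; 50% was also tried. The odds ratio (OR) for AF between strata is in neither document; values of 1 to 5 are assumptions.

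**The plan's own figure.** With k = 2 and pooled rate (0.037 + 2 × 0.16)/3 = 0.119, the standard-care arm needs

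n = [1.960·√(0.119 × 0.881 × 1.5) + 0.8416·√(0.037 × 0.963 + 0.16 × 0.84/2)]² / (0.16 − 0.037)²
= (0.7772 + 0.2699)² / 0.01513 = 72.5, rounded up to 73.

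That gives 73 + 146 = 219, close to the stated 216. Power at 72/144 by the same formula is 79.7%. The calculation contains no stratum term.

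**Power with and without the stratum.** Two pairs of tests were simulated, with allocation balanced within strata: likelihood-ratio logistic regression without and with a stratum term (40,000 runs per scenario), and the Pearson test against the Mantel-Haenszel (MH) test without continuity correction (60,000 to 200,000 runs). Entries are the change in power, in percentage points, from including the stratum.

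| Assumed stratum OR | Logistic, 144:72, 20% STEMI | Logistic, 144:72, 50% STEMI | MH, 144:72, 20% STEMI | Logistic, 120:120, 20% STEMI | MH, 120:120, 20% STEMI |
|---|---|---|---|---|---|
| 1 | +0.2 | +0.1 | −0.1 | 0.0 | −0.5 |
| 2 | +0.2 | +0.8 | −0.1 | +0.1 | −0.3 |
| 3 | +0.8 | +1.6 | +0.5 | +0.2 | −0.1 |
| 5 | +1.8 | +2.6 | +2.0 | +0.7 | +0.3 |

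For example, MH against Pearson at 144:72 with a 20% STEMI share is 82.0% vs 82.1% at OR 1, 82.3% vs 82.4% at OR 2, 83.1% vs 82.6% at OR 3 and 85.0% vs 83.0% at OR 5. Over both STEMI shares and ORs of 1 to 2 at 144:72, the change runs from −0.3 to +0.7 points by MH and +0.1 to +0.8 by logistic regression. Differences of 0.1 to 0.2 points between the logistic models at OR 1 are simulation noise.

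**Type I error.** With a common AF rate of 10% (an assumption) at 144:72, the Pearson test falls from about 4.7% at OR 1 to about 4.1% at OR 5, while MH stays at 4.5% to 5.0%. The 4.7% at OR 1 comes from discreteness, so at OR 3 (about 4.5%) only some 0.2 points are due to the stratum. At 120:120 with a 50% STEMI share, the Pearson test falls from 5.2% to 4.6% over the same range.

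The logistic model with the stratum rejects in 5.0% to 5.6% of null runs at 144:72, so part of its power gain reflects a slightly liberal test.

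**Sparse control events.** Expected AF events in 72 controls: 72 × 0.037 = 2.7. The chance of none is 0.963^72 = 6.6%. In that case ordinary logistic regression has no finite odds ratio, while a Mantel-Haenszel risk difference is still defined.

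**The case against.** The strongest reply is that 3.8 is silent, not wrong. A reader might infer that the regression ignores the stratum and that the test therefore contradicts the design. The text does not support that: an unspecified regression could include MI type. This stands, and the point is limited to what the plan fails to state.

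A reader might also infer that power is certainly lost. That does not follow either. The documents give no AF rate by MI type, the change is close to nil for odds ratios up to 2 at a 20% STEMI share, and at 120:120 the Mantel-Haenszel test is slightly worse than the unadjusted test unless the stratum effect is extreme.

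The conservatism itself needs balance within strata, which requires blocking or something similar. Neither 3.7 nor 4.2 describes it. When the arm split within strata is left to chance, the unadjusted type I error stays near 4.8% for odds ratios of 1 to 5 and the conservatism disappears. A power gain at odds ratios of 3 and above remains at 144:72.

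Finally, replacing the planned regression with a Mantel-Haenszel risk difference as the primary method would be more than the gap requires. That stands too. A covariate in the planned model is enough.

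None of this removes the gap. The plan stratifies on a factor and then does not say whether the primary analysis uses it.

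**Conclusion.** The concern holds in a limited form. Randomisation is stratified by MI type, and the primary analysis is not stated to include that factor. If the regression is run as the two-group comparison described, the cost is conditional: less than 1 point of power at 144:72 for a stratum odds ratio of 1 to 2, up to about 2.6 points at 5, and −0.5 to +0.7 points at 120:120 depending on the method. These figures rest on assumed stratum odds ratios, a STEMI share of 20% or 50%, the plan's AF rates, and allocation balanced within strata.

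A reader might go further and conclude that the primary test is invalid. The calculations do not support that: leaving the stratum out errs, if at all, on the conservative side, and the required sample size does not materially change. This is a minor point. The conflict between 2:1 and 1:1 allocation across 3.7, 3.8 and 4.2 matters more and must be reconciled separately.

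**What to change.** Add to section 3.8: 'The regression comparing 30-day AF between groups will include the randomisation stratum (STEMI vs NSTEACS) as a covariate, and the time-to-event analysis will be stratified by the same factor.' Name the regression model and effect measure in the same place.

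A Mantel-Haenszel analysis stratified by MI type is an acceptable alternative, useful because so few control events are expected. If logistic regression is kept, state what will be done if an arm has no events, for example a penalised (Firth) fit.

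The cost is a sentence or two. No new data or extra patients are needed, since MI type is already on the enrolment form.

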4. FEASIBILITY

4.1 Recruitment

There are approximately 310 STEMI/year in the health region (308-341/year, regional data²²) with at least 4 NSTEACS per 1 STEMI (1240 NSTEACS/year, including transfers, regional data²³). Patients will be excluded based on LVEF>40% (66% ineligible²⁴), pre-existing AF (9%²¹), in-hospital AF (14%⁴), LV thrombus (8%²⁵), and other factors (i.e. heart valves/VTE; uncommon, $\leq 1\%^{26}$). 368 patients/year will meet enrollment eligibility. Using an enrollment rate of 66%, 20 patients will be enrolled per month (10 for intensive) and the target (264 patients) will be met in 13 months.

Patient recruitment will be overseen by Cardiology Research Manager, [name], and Cardiology Clinical Research Coordinator, [name].

Patients will be recruited directly from the Vancouver General Hospital Coronary Care Unit (CCU). The Cardiology research nurses ([name] and [name]) routinely screen patients admitted to the CCU for study eligibility. This process is well-established for a number of ongoing studies that operate in the CCU.

In this study, prospective participants will be identified upon admission to the CCU meeting the eligibility criteria. Study participants will be approached by [name] and [name] for consent to participate in the study.

4.2 Randomization and Blinding

Patients will be recruited from the Vancouver General Hospital Cardiac Care Unit (CCU) and St. Paul's Hospital Cardiac Intensive Care Unit (CICU). Randomization will be performed using a central randomization system (integration through RedCap) in a 1:1 manner, and will be implemented using an online access (RedCap) system. A back-up randomization will be available through sealed envelope in case of database issues. The allocation sequence will be generated by the co-investigator and Database expert (AS). Patients will not be blinded to the monitoring device. Physicians will blinded to patient identity, but will only review results for patients that received the monitoring device.

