3.6 Outcomes

- Primary Outcome: development of atrial fibrillation or flutter lasting ≥30 seconds (consensus definition^{19, 20}) detected using external loop recorder
- 2) Secondary Outcome: anticoagulation prescription, AF-related hospitalization, and a composite secondary outcome of all-cause hospitalization, re-infarction, stroke, and death at 90-days and 1-year after completion of monitoring

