4.6 Research Infrastructure

The coordinating centre is the UBC Division of Cardiology, Cardiology Research at Vancouver General Hospital (located at Gordon and Leslie Diamond Health Care Centre). This research project will be performed at two sites in British Columbia with supervisors at each site (Vancouver General Hospital: JA, KG; St. Paul's Hospital: AK, MD). Each site benefits from a large referral base for STEMI and NSTEACS from across the province. There is established research support for the screening and enrollment of patients (research nurses are supportive). This project is financially supported by the UBC Division of Cardiology, with divisional research funds (CAPP) to support the purchase and donation of 10 Spiderflash monitors to this project.

The steering committee includes the principal investigator and co-investigators listed in this application. Enrollment will be performed by the Cardiology Research staff (AS, JC) and trainee (CC). The endpoint adjudication committee will be attend through consensus of the principal investigator (JA) and trainee (CC). The data management team will include the co-investigator (AS) with expertise in data management and RedCap Database development and the trainee (CC).

The trainee (CC) leading this project has significant research experience, and has participated in multiple prospective and retrospective projects in the field. He has written a review of loop recorders in syncope, and is writing a review of novel technologies for detecting AF. He has received multiple awards, including from the Canadian Stroke Prevention Intervention Network (C-SPIN) and the Cardiac Arrhythmia Network of Canada (CANet), and twice attended the C-SPIN Annual Clinical Trials workshop. The

supporting mentor and supervisors have extensive experience in clinical trials and AF research, and the trainee has collaborated with them on various occasions. Together, these supports and experiences provide an exceptional research environment for the design, coordination, and completion of this research project.

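### The person who generates the allocation sequence is also listed as enrolling patients, so one enroller can know upcoming assignments

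*Combined protocol and SAP*

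**What the plan says.** Section 4.2 sets up central randomization through REDCap and names who makes the list: "The allocation sequence will be generated by the co-investigator and Database expert (AS". It adds a fallback, "A back-up randomization will be available through sealed envelope in case of database issues", without saying who prepares or holds the envelopes. The trial is open to participants: "Patients will not be blinded to the monitoring device".

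Section 4.6 names the enrollers: "Enrollment will be performed by the Cardiology Research staff (AS, JC) and trainee (CC". The same section places the database co-investigator, under the same initials, on the data management team together with the trainee.

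Section 3.7 links the two steps: "Upon enrollment, patients will be randomized". On consent, section 4.1 says: "Study participants will be approached by [name] and [name] for consent to participate in the study". The names there are removed from the public copy.

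**The concern.** Allocation concealment requires that whoever decides on a patient's entry cannot know the next assignment. A central system does this for users who cannot see the list. It does nothing for the person who produced the list. Here that person appears among the enrollers.

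If the enrolment role includes choosing whom to approach, or when to register someone who has agreed, those choices can depend on the coming assignment. Selection of this kind happens before randomization, so the intention-to-treat analysis in section 3.8 does not protect against it, and covariate adjustment corrects only for what was measured.

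The outcome most exposed is the secondary one in section 3.6: "a composite secondary outcome of all-cause hospitalization, re-infarction, stroke, and death at 90-days and 1-year after completion of monitoring". It depends directly on equal baseline risk. So do the between-group comparisons of mortality and re-hospitalization that the Data Monitoring Committee reviews under section 4.8.

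**Working it through.** The point rests on who does what, so the first step is to set the roles side by side.

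| Task | Who | Section |
|---|---|---|
| Generate the sequence | Database co-investigator | 4.2 |
| Enrol patients | Database co-investigator (same initials), one other research staff member, trainee | 4.6 |
| Screen admissions; seek consent | Research nurses; two people (names removed) | 4.1 |
| Data management team | Database co-investigator, trainee | 4.6 |
| Data entry | Principal investigator, trainee, database co-investigator | 4.7 |
| Adjudicate endpoints | Principal investigator, trainee | 4.6 |
| Data Monitoring Committee | Two co-investigators, also site supervisors | 4.8, 4.6 |
| Prepare and hold envelopes | Not stated | 4.2 |

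1. **Same person?** The match is by initials. Section 4.6 uses them in both the enrolment and the data management sentences without distinguishing two people. The ordinary reading is one person with both roles.
2. **Is the list hidden from its maker?** No section says so, keeps the maker from enrolling, or gives custody to someone independent.
3. **Other routes.** The trainee enrols and is also on the data management team. Whether the trainee can see the allocation table is not stated.
4. **Could knowing the next assignment affect timing?** The study has 10 monitors (sections 4.3 and 4.6), each worn for 30 days. At 20 enrolments a month, 1:1 allocation needs 20 × 1/2 = 10 monitors, which leaves no slack. The 2:1 allocation in section 3.7 needs 20 × 2/3 = 13.3. An enroller who knew the next assignment would have an ordinary logistical reason to delay or advance a registration. This is an inference from the plan's figures, not evidence that it would happen.
5. **Primary outcome, for scale.** The planned difference is 16% − 3.7% = 12.3 percentage points. It compares 30 days of monitoring with 12-lead ECGs before discharge and at follow-up, so most of it should come from detection.
6. **Cost of removing the generator from enrolment.** The plan's rate reproduces: 368 eligible a year × 0.66 / 12 = 20.2, in line with "20 patients will be enrolled per month" in section 4.1. With three enrollers the load is 20 / 3 = 6.7 each per month. With two it is 20 / 2 = 10, an increase of 3.3. Even sharing is an assumption, since the plan gives no split.

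The bias itself cannot be calculated. The documents do not say how many patients the generator would enrol or whether anyone would consult the list.

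**The case against.** The strongest reply is that this is an opportunity and not a demonstrated flaw. The match rests on initials. Enrolment in section 4.6 may mean only registering patients whom the research nurses have screened and others have consented, and the names that would settle this are removed from section 4.1. To exploit the list, the generator would have to consult it and keep track of position within the STEMI and NSTEACS strata. Section 4.4 calls the study a pilot, the primary contrast is unlikely to arise from this overlap, and section 3.8 plans no specific analysis of the composite.

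The workload figures can also be questioned. They size the staffing cost and not the defect. The rate of 20 a month comes from a calculation in section 4.1 that excludes patients with LVEF above 40%, which is not among the criteria in sections 3.4 and 3.5. Dividing by three ignores the separate screening and consent staff and assumes work can be shared across the two sites.

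Much of this stands. It limits the weight of the point and makes the workload figures rough. It does not remove the overlap: stratified central randomization makes the list harder to use, but its maker can still know it. If the generator only registers patients already consented and has no say over timing, a sentence saying so would largely answer the point.

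**Conclusion.** The concern holds as a risk of selection bias. On the ordinary reading of sections 4.2 and 4.6, one of three listed enrollers can know upcoming assignments, and the plan contains no safeguard against it. No breach is shown and the size of any bias is unknown. The conclusion assumes that the shared initials denote one person. Harm further requires that this person influences whom to approach or when to register, which the public documents do not settle.

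The overlap alone is unlikely to produce the primary difference, but it weakens the basis for comparing clinical outcomes between groups. It should be corrected because the correction is cheap and concealment cannot be restored once patients have been randomized.

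**What to change.** Make one of two changes before the first randomization:

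- **Section 4.6:** remove the sequence generator from the list of enrollers; or
- **Section 4.2:** have the list generated and loaded by an existing team member who does not screen, seek consent, enrol, adjudicate endpoints or sit on the Data Monitoring Committee. This rules out the principal investigator, the trainee and the two committee members. One St. Paul's site supervisor is given no conflicting role in the documents, so a candidate appears to exist.

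In either case, add a sentence to section 4.2 that nobody who enrols can view the REDCap allocation table or hold the back-up envelopes. It is needed under both options: the trainee enrols and is on the data management team, and under the second option the database co-investigator would too. Sections 3.7 (2:1) and 4.2 (1:1) must also be reconciled before any list is made.

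The first option costs the two remaining enrollers about 3.3 more enrolments each per month, if evenly shared. The second adds no enrolment work but asks someone else to prepare and load the list. Patients, sample size and analysis do not change.
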